The Analytic Core will securely share the contact information of eligible participants with SRV sites via a secure Box or Microsoft OneDrive account. SRV staff will enter the eligible participant into SMART for scheduling and contact participants to schedule an in-person visit at the SRV or an online enrollment visit. Study staff also have the option of scheduling and completing some study visit activities in person and some of the study visit activities online to provide flexibility during the COVID-19 pandemic and afterwards and to be responsive to participant needs.

YYA who screen eligible and provide contact information will be contacted by SRV staff and provided with information about the date and time of the focus group (in Phase 1) or to schedule an in person or online baseline enrollment visit (in Phase 2). An email will be sent to potential focus group participants immediately after they are scheduled for the focus group that includes the focus group date, time, location and staff contact information. Potential focus group participants will be sent a reminder three days prior to the focus group, as well as on the day of the focus group.

YYA who screen ineligible (see section 4.2 for exclusion criteria) will be informed at the conclusion of the screener that they are not eligible for the study.

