5.1.2 RCT Enrollment

Screening procedures are explained above in section 4.4. All persons who screen eligible for the study will be guided through the informed consent process (section 4.5) on the day of their enrollment appointment. Research staff administering the consent process will pay particular attention to whether the potential participant appears confused or otherwise unable to complete the informed consent process, and will stop enrollment of that participant in the RCT.

Following informed consent, trans YYA will go through baseline assessment procedures of having HIV testing, blood microsampling analysis for those who self-report PrEP use, screening for STIs and drug use through a urine screen (note: HIV testing is the only required biological specimen collection, all others are voluntary), and the survey measures through an ACASI. Biological specimen collection may be done in person during the study visit or via self collection kits mailed to participants. For mailed self collection, the biological specimens may be collected after the baseline enrollment visit and must be returned within 90 days. After randomization, participants will receive more information about the arm they are randomized into (e.g. how to use the WebApp, the frequency of text messages, or how to access the resources and information). For in person enrollment visits, participants will be deemed enrolled in the study after baseline procedures and the enrollment visit are completed. For online enrollment visits, participants will be deemed enrolled in the study after they are randomized and onboarded.

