5.2 Randomization Procedures

For the purpose of Phase 1 focus groups, participants will not be randomized.

Randomization for the RCT is explained in section 3.3.2.

During the RCT, after completion of the baseline ACASI, participants will be randomized 1:1:1 to the Text+Step intervention or App+Step intervention or control condition, based on a randomization sequence developed by the AC lead statistician and loaded into DFexplore (see section 7.4.1 for more details on DFexplore). The randomization sequence will be stratified by city and use random permuted blocks of size 3.

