5.3.3 RCT

Enrollment for the RCT will be conducted in person or online at 5 SRVs (Boston, Houston, Los Angeles, New York, and Philadelphia). Online study visits may be carried out via an online videoconferencing software, such as Zoom (see Section 7.3.6 for description of the Zoom platform) or a comparable platform.

Enrollment procedures are anticipated to last approximately 120 minutes and consists of informed consent/assent, the baseline ACASI survey, and HIV, STI and drug screen testing, and blood microsampling for those who self-report PrEP use (of the biological specimen collection, only HIV

testing is mandatory). For online enrollment visits, some or all of the biological specimen collection may be done via mailed self-collection kits after the enrollment visit. Participants, if they choose to do so, will be able to meet with research staff via live, secure video chat, to answer questions about the at-home self-collection kit components and procedures. Particularly, study staff will be able to answer questions and go over results of rapid HIV test results if participants prefer to self-administer a rapid test in addition to or in lieu of a lab processed HIV test. Rapid HIV test results will be confirmed with research staff via secure video chat, or by uploading a photo of the test results to a secure online survey hosted by Alchemer. During enrollment, participants will be randomized into either the Text+Step arm, the App+Step arm, or the information-only (i.e. "Info") arm. Participants randomized into the Text+Step arm will be given information about the frequency of text messages they should expect. Participants randomized into the App+Step arm will be guided by research staff to log onto the WebApp for the first time and obtain basic information on how to navigate the app. Participants randomized into the "Info" arm will learn how they will gain access to the information available in that arm and the basic description of that information. At the end of the enrollment visit, all participants will be invited to schedule their 3-month follow-up appointment.

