7.4 Data Submission

7.4.1 CRFs

Although the iTech projects will involve substantial online follow-up, CRFs will be used to collect key study visit data (e.g., enrollment and randomization assignment), study milestones such as completion or discontinuation, study laboratory results, and adverse events (AE). AC staff will work with study investigators and the MC to develop and design the CRFs. During study conduct, the SRVs will maintain the CRFs in secured locations, and transmit CRF data to the AC either electronically using DFExplore or by submitting scanned paper forms using DFSend. DFExplore and its DFdiscover platform is a leading multi-site database environment for HIV RCT that can receive and transcribe CRF data via scanned PDFs, or allow for direct electronic data entry. It provides for monitoring form completion and data quality, and a system for data querying and resolution with SRVs, while maintaining an audit trail. The AC uses DFExplore for MSM studies and RCTs and data is maintained by the parent company DF/net on a cloud-based server with Microsoft Azure.

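### One fixed, printed block size of 3 within city lets site staff who learn the assignments deduce one allocation in three in advance, which permits selection bias

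*Combined protocol and SAP*

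**What the plan says.** Section 5.2 specifies that "after completion of the baseline ACASI, participants will be randomized 1:1:1 to the Text+Step intervention or App+Step intervention or control condition". The list is prepared centrally, by the Analytic Core's lead statistician, and held in DFexplore. On the block scheme the section says: "The randomization sequence will be stratified by city and use random permuted blocks of size 3". No second block size is given, and the protocol does not say that the size is withheld from sites.

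The strata match the sites one to one. Section 5.3.3 says: "Enrollment for the RCT will be conducted in person or online at 5 SRVs (Boston, Houston, Los Angeles, New York, and Philadelphia"), and Section 4.1.3 lists one institution for each of these cities. Staff at a site can therefore observe the whole sequence of their own stratum.

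The documents never use the term open label, but site staff learn the arm. Section 5.3.3 has them onboard participants: "Participants randomized into the App+Step arm will be guided by research staff to log onto the WebApp for the first time". Section 7.4.1 says that "CRFs will be used to collect key study visit data (e.g., enrollment and randomization assignment"), and has the sites maintain those forms.

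The same staff influence who is enrolled and when. Section 4.4 says: "SRV staff will enter the eligible participant into SMART for scheduling and contact participants to schedule an in-person visit at the SRV". Online visits are booked in the same way. Under Section 5.1.2 they look for confusion during consent "and will stop enrollment of that participant in the RCT". Section 4.2.3 adds an exclusion for people judged unwilling or unable to comply.

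**The concern.** Three is the smallest block that can hold three arms at 1:1:1, and a block that small leaves no uncertainty about its last place. Once two people in a city's block have been assigned, the third arm is fixed. After one, only two arms remain. Anyone who knows the block size and keeps a count can work this out before the next candidate is scheduled, consented or turned away.

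Staff may also know something about a candidate's risk by then. Section 4.4 allows them to administer the screener and record the answers. Section 4.3 allows chart review and direct contact with former participants. If higher- or lower-risk people were brought in when a particular arm was due, the comparison of Text+Step or App+Step with Info would be biased. The outcomes in Section 10.3.2 are mostly self-reported sexual behaviour. Confirmed STI diagnoses and blood microsampling for PrEP are included, but the Study Abstract makes those specimens optional, so they are only a partial safeguard.

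**Working it through.** The plan states no predictability figure, so there is none to reproduce.

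**Inputs.** Three arms, 1:1:1, fixed blocks of 3, five cities (Sections 5.2 and 5.3.3). Planned N = 275; arm targets 108, 83 and 83 (Section 3.2). Assumption: equal recruitment, 275/5 = 55 per city. The guesser knows all earlier allocations in the city and names the arm with most places left.

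**Fixed blocks of 3.** The chance of a correct guess is 1/3 at the first place, 1/2 at the second and 1 at the third:

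(1/3 + 1/2 + 1)/3 = 11/18 = 61.1%, against 33.3% by chance.

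One place in three is certain.

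**In participants.** 55 per city gives 18 complete blocks and one person over, so 5 × 18 = 90 of 275 assignments are known in advance. On a plan of 83 per arm the figure is 83 of 249. Expected correct guesses are about 275 × 11/18 = 168, against 275/3 = 92 by chance. Allowing for the incomplete last block, each city gives 18 × 11/6 + 1/3 = 33.3 correct guesses, or 33.3/55 = 60.6%.

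**Alternatives.** Fixed sizes were calculated exactly for complete blocks. Varying sizes were simulated (55 per city, 3000 runs, sizes equally likely) with an optimal guesser who knows the possible sizes but not their order.

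| Scheme | Certain in advance | Guessed correctly |
|---|---|---|
| Fixed 3 | 33.3% | 61.1% |
| Fixed 6 | 20.0% | 56.1% |
| Fixed 9 | 14.3% | 53.2% |
| Random 3/6 | 8.3% | 57.2% |
| Random 6/9 | 4.9% | 53.7% |
| Random 3/6/9 | 3.7% | 54.8% |

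The main gain from varying sizes is in certain assignments; guessing improves less.

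**Arm targets.** 108 + 83 + 83 = 274, one short of the stated 275. Complete 1:1:1 blocks cover at most 3 × 83 = 249 people. The other 108 − 83 = 25 Text places cannot come from such blocks, yet Sections 3.3.2 and 5.2 still say 1:1:1. The figures for blocks of 3 therefore apply only while those blocks are in use.

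**What a retrospective check must look at.** Third places are the predictable ones, and each arm falls there with probability 1/3. Suppose staff shift baseline risk by +d when Text is due and by −d when Info is due. Pooled over arms, the expected third-minus-first difference is (d − d + 0)/3 = 0. Steering into one arm alone shows up as only d/3. A pooled comparison could therefore reassure falsely; the check has to be arm by position.

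**The case against.** The sequence is made centrally and held in DFexplore, and assignment follows consent and the baseline ACASI. Nobody at a site can read the list, and the detailed risk data are self-entered by the participant. On the online route, eligible candidates reach the site through the Analytic Core. Steering would need someone to tally allocations and then act through scheduling or exclusion, and the documents do not say that anyone does. Section 10.3.2 already adjusts for baseline covariates. Varying the block size lowers correct guessing only from 61% to about 55%.

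Most of this is fair, but it does not remove the weakness. Central custody protects the list; it does not stop a reader of Section 5.2 from deducing the next arm before deciding whom to book. Staff-administered screening, chart review and contact with former participants leave routes to prior knowledge of risk. The small change in overall guessing conceals a fall in certain assignments from 33% to about 4%.

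Three stronger readings are tempting, and the documents do not support them:

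- A reader might infer that concealment fails outright for a third of participants. The documents show predictability for someone who tallies, not that anyone tallied or acted.
- A reader might infer that steering could never be found afterwards. The baseline ACASI precedes randomization, so steering on measured risk can be examined and adjusted for. Only steering on unmeasured traits, such as motivation, would escape.
- A reader might infer that every outcome is self-reported and that everyone knows the arm. Some outcomes have biomarkers, and the documents do not say whether laboratory staff or analysts know the arm.

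**Conclusion.** The concern holds as one of opportunity. While 1:1:1 blocks of 3 are in use, a site staff member who tallies allocations knows one assignment in three in advance (about 90 of 275 under equal recruitment) and guesses 61% correctly.

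This rests on three things: staff learn each assignment, which is inferred from onboarding and form handling; they know the block size, which is printed; and they have some say over who is enrolled next. No bias in the contrast with Info can be calculated from the documents, because that would need an assumed amount of steering.

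It would also go too far to say that the 25 extra Text places were fully predictable. That would be so if they were all filled after the other arms closed, but the documents do not describe how they are allocated. The point should be corrected because the remedy is cheap and the allocation text needs revision anyway.

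**What to change.** 1. Reconcile the 1:1:1 wording in Sections 3.3.2 and 5.2 with the 108/83/83 targets in the Study Abstract, the Figure 1 note and Section 3.2. State how the additional Text places are allocated.
2. For any remaining allocations, use randomly varying block sizes within city that are multiples of the reconciled ratio (for example 3, 6 and 9 if it is 1:1:1). Balanced blocks cannot themselves deliver 108/83/83, so step 1 comes first. Only the Analytic Core should know the sizes, and they should be removed from the site-facing protocol.
3. For allocations already made, plan an arm-by-position check: do baseline risk and PrEP use differ by arm among third-in-block assignments compared with first-in-block ones? With about 90 third places, or 90/3 = 30 per arm, a null result would be weak reassurance and should be reported as such.
4. Name baseline risk and baseline PrEP use as LTMLE covariates in Section 10.3.2, which currently names none.

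The cost is a new sequence to load into DFexplore, a protocol edit, and slightly looser balance within a city at any moment. Steps 3 and 4 need no new data and remain useful if enrolment has ended.

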5.3 Intervention/Investigation Procedures

5.3.1 Focus Groups

Focus groups will be conducted in person and at 4 SRVs (Houston, Los Angeles, New York, and Philadelphia). Two focus groups will be conducted at each of the 4 SRVs. Focus groups are anticipated to last approximately 120 minutes, and light refreshments and food will be served at each group. Research staff will conduct the focus groups. The focus groups conducted in New York and Philadelphia will be used to gain feedback from trans YYA on the text messaging intervention of TechStep, while the focus groups in Houston and Los Angeles will be used to gain feedback on the WebApp. All focus groups will be audio recorded (equipment provided by the research staff). The Protocol Chair will coordinate with SRV staff to arrange participant compensation at the end of each focus group. A minimum of 3 persons must be present at the beginning of the focus group to conduct the focus group. If 1 or 2 persons are present at the beginning of the focus group, we will ask that it be rescheduled and they will be compensated for transportation costs.

5.3.2. Focus Group Recruitment

Focus group participants will be recruited from SRVs, other community settings, online, and through peer referrals. Specifically, focus group participants may be recruited through poster advertisement placed at each SRV or at community sites that collaborate with the SRV. The posters will contain details about how to contact a Research Assistant for further information regarding the focus groups. Ads will be posted on social media and with brief information about the purpose of the focus groups as well as information about compensation. Interested individuals can screen online or can email the SRV Research Assistant to find out more and get screened for eligibility over the telephone or in-person. When a participant screens eligible to participate in a focus group, they will be asked to refer any friends who are also trans YYA. If the SRV has a YAB, some participants may be recruited directly from the YAB

5.3.3 RCT

Enrollment for the RCT will be conducted in person or online at 5 SRVs (Boston, Houston, Los Angeles, New York, and Philadelphia). Online study visits may be carried out via an online videoconferencing software, such as Zoom (see Section 7.3.6 for description of the Zoom platform) or a comparable platform.

Enrollment procedures are anticipated to last approximately 120 minutes and consists of informed consent/assent, the baseline ACASI survey, and HIV, STI and drug screen testing, and blood microsampling for those who self-report PrEP use (of the biological specimen collection, only HIV

testing is mandatory). For online enrollment visits, some or all of the biological specimen collection may be done via mailed self-collection kits after the enrollment visit. Participants, if they choose to do so, will be able to meet with research staff via live, secure video chat, to answer questions about the at-home self-collection kit components and procedures. Particularly, study staff will be able to answer questions and go over results of rapid HIV test results if participants prefer to self-administer a rapid test in addition to or in lieu of a lab processed HIV test. Rapid HIV test results will be confirmed with research staff via secure video chat, or by uploading a photo of the test results to a secure online survey hosted by Alchemer. During enrollment, participants will be randomized into either the Text+Step arm, the App+Step arm, or the information-only (i.e. "Info") arm. Participants randomized into the Text+Step arm will be given information about the frequency of text messages they should expect. Participants randomized into the App+Step arm will be guided by research staff to log onto the WebApp for the first time and obtain basic information on how to navigate the app. Participants randomized into the "Info" arm will learn how they will gain access to the information available in that arm and the basic description of that information. At the end of the enrollment visit, all participants will be invited to schedule their 3-month follow-up appointment.

Participants can schedule and attend a 3-month follow-up visit in person or online as early as 14 days prior to the calendar date that falls three months after their enrollment date, and as late as 75 days after the calendar date that falls three months after their enrollment date. At the 3-month follow-up visit, participants will undergo additional HIV, STI and drug screen testing, blood microsampling for those who report PrEP uptake or continued PrEP use, as well as take another ACASI survey. Biological specimen collection may be done in person during the study visit or via self-collection kits mailed to participants. For mailed self-collection, the biological specimens may be collected and returned at any point during the visit window. Participants, if they choose to do so, will be able to meet with research staff via live, secure video chat, to answer questions about the at-home self-collection kit components and procedures. Particularly, study staff will be able to answer questions and go over results of rapid HIV test results if participants prefer to self-administer a rapid test in addition to or in lieu of a lab processed HIV test. Rapid HIV test results will be confirmed with research staff via secure video chat, or by uploading a photo of the test results to a secure online survey hosted by Alchemer. Participants in the technology-based intervention groups (i.e. the Text+Step or the App+Step arm) that do not reduce sexual risk behaviors or self-report a recent STI diagnosis and do not initiate PrEP or adhere to PrEP at effective levels will be randomized 2:1 into either additional eCoaching with their technology-based intervention or remain with their originally assigned intervention. Stepping will be determined using a series of questions: 1) participants that self report PrEP adherence (4+ doses taken per week for each of the past 2 weeks) will not step, otherwise; 2) participants who self-report a new STI (syphilis, chlamydia, or gonorrhea) diagnosed outside of the study in the past 3 months will be eligible for step by randomization, otherwise; 3) participants who self-report sexual risk in the form of: a) condomless anal or vaginal sex, b) sex with exchange partners, c) sex while feeling the effects of stimulants (methamphetamine, powder cocaine, or crack cocaine) or d) sex after binge drinking (5+ drinks at one time) in the past three months will be eligible for step by randomization. Those that are randomized to step up to additional eCoaching will meet the eCoach online at the 3-month visit or during the 3-month visit window for an introductory visit and to schedule their next eCoaching session.

Participants can schedule and attend a 6-month follow-up visit in person or online as early as 14 days prior to the calendar date that falls six months after their enrollment date, and as late as 75 days after the calendar date that falls six months after their enrollment date. At the 6-month follow-up visit, participants will undergo additional HIV, STIs and drug screen testing, blood microsampling for those who report PrEP uptake or continued use, as well as take another ACASI survey. Of the biological specimen tests, only HIV testing is required, however the others (i.e.,

STI testing, uring screening, and blood microsampling for those reporting PrEP use) are encouraged. Biological specimen collection may be done in person during the study visit or via self-collection kits mailed to participants. For mailed self-collection, the biological specimens may be collected and returned at any point during the visit window. Participants, if they choose to do so, will be able to meet with research staff via live, secure video chat, to answer questions about the at-home self-collection kit components and procedures. Particularly, study staff will be able to answer questions and go over results of rapid HIV test results if participants prefer to self-administer a rapid test in addition to or in lieu of a lab processed HIV test. Rapid HIV test results will be confirmed with research staff via secure video chat, or by uploading a photo of the test results to a secure online survey hosted by Alchemer. The active intervention period ends after 6 months, and therefore participants will no longer have access to their intervention to which they were assigned after month 6.

Participants can schedule and attend a 9-month follow-up visit as early as 14 days prior to the calendar date that falls nine months after their enrollment date, and as late as 90 days after the calendar date that falls nine months after their enrollment date. Participants will return to the SRV at the 9-month follow up for HIV, STI, and drug screen testing, blood microsampling for those report PrEP uptake or use, as well as a final ACASI to measure sustained effects of the intervention. Of the biological specimen tests, only HIV testing is required, however the others (i.e. STI testing, uring screening, and blood microsampling for those reporting PrEP use) are encouraged. Biological specimen collection may be done in person during the study visit or via self-collection kits mailed to participants. For mailed self-collection, the biological specimens may be collected and returned at any point during the visit window. Participants, if they choose to do so, will be able to meet with research staff via live, secure video chat, to answer questions about the at-home self-collection kit components and procedures. Particularly, study staff will be able to answer questions and go over results of rapid HIV test results if participants prefer to self-administer a rapid test in addition to or in lieu of a lab processed HIV test. Rapid HIV test results will be confirmed with research staff via secure video chat, or by uploading a photo of the test results to a secure online survey hosted by Alchemer.

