Although systematic review indicates that mobile health interventions are particularly efficacious at increasing HIV protective behaviors among vulnerable and key HIV risk populations such as trans youth,²⁸ a recent systematic review revealed that only 18% of mobile phone-based HIV prevention/care interventions provide any information tailored to LGBT populations, and none were tailored specifically to trans individuals.²⁹ One digital intervention designed for LGBT youth, but not specifically tailored for trans youth, successfully increased safer sex outcomes among participants,³⁰ and another intervention designed for young African American/Black MSM and trans women, but was not specifically for trans women, demonstrated significant improvements in participant social support, social isolation, and depressive symptoms.^{31,32} The TechStep study will fill a critical gap in the scientific advancement of technology-based interventions for trans youth by a) creating the first technology-based trans youth-specific HIV prevention interventions optimized for mobile phone delivery; and, b) employing the two intervention delivery modalities identified as most promising for use among trans YYA (i.e., text messaging and mobile app).

As part of the UNC/Emory Center for Innovative Technology (iTech), we propose to test the efficacy of TechStep for trans YYA. In this 4-year study, 275 high-risk trans YYA between the ages of 15-24 will be randomized to receive text messaging, a WebApp, or an information-only control intervention for 6 months, with assessments occurring at baseline and 3-, 6- and 9-months. YYA who do not evidence improvements in sexual risk and/or PrEP uptake at the 3-month assessment will be randomized to either receive weekly eCoaching sessions in addition to their assigned text messaging or WebApp intervention, or remain in the original intervention in a 2:1 ratio. The primary endpoint is reduced sexual risk behaviors and/or PrEP uptake, adherence and persistence at month 6.

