1.2.3 RCT of TechStep

A 3-arm RCT of TechStep will be conducted with the following conditions: 1) a text messaging stepped care intervention, 2) a WebApp stepped care intervention, and 3) a low-intensity information control group. Those in either of the active technology-based intervention conditions who do not report a reduction in sexual risk and have not started PrEP, or those who report a reduction in sexual risk but have discontinued PrEP since their last assessment will be randomized to either step up to receive the technology-based intervention (text or WebApp) plus weekly eCoaching sessions or to remain on the original intervention.. The control group will consist of information about trans health, HIV/STI information and local resources for trans persons. A RCT was chosen since it is the gold standard for assessing the effectiveness of an intervention under tightly controlled conditions. The intervention and control groups will have access to information and intervention content for 6 months, with ACASI performed at baseline, and every 3 months thereafter for 9 months (i.e., 3-month, 6-month, & 9-month follow-up assessments). At all follow-up assessments, trans YYA will be assessed for their sexual risk behaviors and PrEP uptake, adherence and persistence. Assessments will include self-reported behavioral data, and biomarkers for HIV, STIs, current drug use, and PrEP adherence and persistence.

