Trans YYA will be recruited from 5 SRVs (Boston, Houston, Los Angeles, New York, and Philadelphia) to participate in a 3-arm RCT to determine immediate and sustained effects of the Text+Step intervention versus the App+Step intervention compared to an information-only control condition (“Info” arm). All participants will receive one of the interventions for 6 months, with assessments occurring at baseline and every 3 months thereafter until month 9. Trans YYA randomized to either of the technology-based intervention arms (Text or WebApp) will be evaluated at the 3-month follow-up assessment time points to determine if they remain at the current level of intervention, or if they are eligible for randomization to also receive eCoaching sessions in addition to their originally assigned intervention. All participants assigned to the Text+Step intervention arm will begin with the text messaging intervention. Participants assigned to the App+Step intervention arm will begin with the WebApp intervention. At the first follow-up assessment time point, information about their sexual behavior in the past 3 months and whether they began or stopped using PrEP will be used to determine if they require a more intensive intervention approach. Participants who do not demonstrate intervention responsiveness at the 3-month follow-up assessment will be re-randomized, in a 2:1 ratio, to either remain in the original technology-based intervention (i.e., Text or App) or add eCoaching to the original technology-based intervention (i.e., Text+eCoaching or App+eCoaching). This re-randomization will allow for a comparison of intervention effects between the technology-based interventions (i.e., text or app) plus eCoaching to the technology-based intervention alone. The control condition will receive the same information-only intervention for the entire 6-month intervention period.

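### Do the wide 3- and 6-month visit windows spoil the eCoaching comparison or make the cumulative outcome count days twice?

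*Combined protocol and SAP*

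**What the plan says.** Section 5.3.3 allows the 3-month visit from 14 days before the target date and "as late as 75 days after the calendar date that falls three months after their enrollment date". The 6-month visit has a window of the same width and may take place "as early as 14 days prior to the calendar date that falls six months after their enrollment date". Both windows are counted from enrolment.

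Section 3.1 (Phase 2) places the second randomisation at the first follow-up: "Participants who do not demonstrate intervention responsiveness at the 3-month follow-up assessment will be re-randomized, in a 2:1 ratio". Under Section 5.3.3, those stepped up "will meet the eCoach online at the 3-month visit or during the 3-month visit window for an introductory visit". Sessions are weekly (Section 1.1).

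On the end of the intervention, Section 1.2.3 says that the groups "will have access to information and intervention content for 6 months", and Section 5.3.3 says that "participants will no longer have access to their intervention to which they were assigned after month 6".

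On the outcome, Section 1.1 states: "The primary endpoint is reduced sexual risk behaviors and/or PrEP uptake, adherence and persistence at month 6". Section 10.3.2 models accumulated sexual risk behaviour at successive time points by LTMLE, adjusting for baseline and time-varying covariates that it does not list. It also names rates of condomless sex among the outcomes. A three-month lookback is documented only for the first follow-up and its stepping questions, where participants reporting sexual risk "in the past three months will be eligible for step by randomization".

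**The concern.** Two things look wrong. First, a participant seen at the end of the 3-month window has little time for weekly coaching before access stops, while one seen at the start has about a quarter of a year. Aim 3 puts both into one contrast, and the stepped part of Aim 2 is affected too. A null result might then reflect coaching that was barely received.

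Second, the two visits can fall almost together or about six months apart. If each report looks back three months and the reports are added, some days would be counted twice in some participants and other days missed in others. Section 10.2.2 expresses the target effect as encounters over the whole study, so the length of time counted bears on the outcome scale. Section 10.3.2 has no visit date, offset or denominator that visibly deals with this, and month 6 is the primary time point.

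**Working it through.** The plan's one computed figure nearby is power above 80% for 1.5 fewer risky encounters (Section 10.2.2). It cannot be reproduced, because no standard deviation or significance level is given. Nothing below depends on it.

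**Inputs.** Windows of -14 to +75 days around M3 and M6, the dates three and six calendar months after enrolment (Section 5.3.3). M6 minus M3 is 89 to 92 days, depending on the enrolment date.

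**Possible coaching time** = M6 minus the 3-month visit date, assuming that access ends on M6.

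| 3-month visit | Days to M6 | Weeks |
|---|---|---|
| M3 - 14 | 89 + 14 = 103 to 92 + 14 = 106 | 14.7 to 15.1 |
| M3 | 89 to 92 | 12.7 to 13.1 |
| M3 + 30 | 59 to 62 | 8.4 to 8.9 |
| M3 + 75 | 14 to 17 | 2.0 to 2.4 |

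These are upper bounds, since the introductory session may come later than the visit.

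**Gap between the two visits.** Shortest: (M6 - 14) - (M3 + 75) = 89 - 89 = 0 to 92 - 89 = 3 days. Longest: (M6 + 75) - (M3 - 14) = 89 + 89 = 178 to 92 + 89 = 181 days.

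**Overlap of the two reports** = max(0, recall length - gap). The recall period at month 6 is not stated, so the range has to be shown:

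- Fixed 91 days: largest overlap 91 - 3 = 88 to 91 - 0 = 91 days. At the longest gap, 178 - 91 = 87 to 181 - 91 = 90 days go unreported. With the month-6 visit on target, overlap is 29-32 days if the 3-month visit is at +30 and 74-77 days if it is at +75.
- Fixed 30 days: largest overlap 30 - 3 = 27 to 30 - 0 = 30 days.
- Since the last visit: overlap 0. The second report alone then covers between 0-3 and 178-181 days, but a running total counts each day since enrolment once, up to the 6-month visit.

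**Would an overlap correction help?** Take reports A and B, each with recall R, sharing o days. Spread each evenly over its days, average the two daily rates on shared days, divide by distinct days, and scale to 2R days.

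- Total = (A + B)/R x (R - o) + (A + B)/(2R) x o = (A + B)/R x (R - o/2).
- Distinct days = 2R - o = 2(R - o/2).
- Rate = (A + B)/(2R), so the scaled result is A + B for every o.

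Example: A = 10, B = 4, R = 91, visits on days 121 and 182, so o = 91 - 61 = 30. Total = 14/91 x 76 = 11.69; distinct days = 152; 11.69/152 x 182 = 14.0, which is the plain sum. The result moves only when the first report reaches back before enrolment: visits on days 77 and 168 give 13.5. With a fixed recall, this adjustment therefore gains nothing for overlap.

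**Bias.** The 3-month visit date is known when re-randomisation takes place, so its distribution is the same in expectation in the coached and uncoached groups. Unequal coaching time weakens the average contrast; it does not confound it.

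**The case for a change.** The strongest case for a change is that some definition is needed under every recall period. A fixed lookback can overlap or leave gaps, and a since-last-visit lookback gives intervals of unequal length. The windows are also wide relative to the coaching period: a visit at +30 already removes 30 of 89-92 days, about a third. Naming the recall period, the construction of the running total and 3-month visit timing as a covariate would take only a few lines. An Aim 3 analysis restricted to earlier 3-month visits would show any dilution.

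The facts in this stand, and the missing details would be useful to have written down. They do not make the plan wrong. Visit timing fits within the baseline and time-varying covariates that Section 10.3.2 already allows, and its reference to rates leaves room for a denominator. The endpoint in Section 1.1 is stated at month 6 and need not be a sum. Section 8.1 has staff contacting participants before the target date, which works against very late visits.

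The restricted analysis would be an optional extra with an arbitrary cut-off. At +30 days it would keep 45/90 = 50% of re-randomised participants if visits were spread evenly over the window, or 1 - 45²/(89 x 75) = 70% if they followed a triangle peaked on the target date; both patterns are assumed.

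Nor do the passages contradict one another: late stepping, access ending after month 6 and a month-6 endpoint can all hold together.

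**Conclusion.** No change follows. The windows permit about 2 to 15 weeks between re-randomisation and calendar month 6, and 0-3 to 178-181 days between the two visits. How often anything near these limits occurs is not given. The effect on Aim 3, a secondary aim, is possible dilution of a comparison that stays protected by re-randomisation. It estimates the benefit of eCoaching as delivered under flexible visits, a fair trade-off for retaining participants who are hard to reach.

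Double counting is not established. It needs a fixed lookback at month 6 and added reports, and the overlap ranges from 0 to about 91 days according to an unstated recall period. The averaging correction reproduces the plain sum. The recall period, the construction of the cumulative outcome and the choice of timing covariates are details that analysts can fill in sensibly within Section 10.3.2.

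This rests on access ending at calendar month 6 (no separate end date for eCoaching is given) and on the 3-month visit date being fixed before re-randomisation. The size of any dilution cannot be calculated from the documents.
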